AIMS (1) Determine the anxiety levels of women with suspected endometrial cancer
(2) Determine factors affecting anxiety levels

OUTCOME MEASURES Primary outcome measures:
(1) Anxiety levels of women with suspected cancer

Secondary outcome measures:
(1) Factors affecting anxiety level

POPULATION 250 women referred to rapid access clinic with postmenopausal bleeding or intermenstrual bleeding.

ELIGIBILITY All women presenting to rapid access gynaecology clinic with postmenopausal bleeding or intermenstrual bleeding

EXCLUSION Anyone lacking capacity. <18years old. Pregnant. Any contra-indication carry out a biopsy

DURATION 1 year

1. INTRODUCTION

1.1 BACKGROUND

Endometrial cancer is a tumour originating in the endometrium (womb lining); it is the most common gynaecological cancer in the UK. In 2012, there were almost 100,000 new cases diagnosed in Europe. The lifetime risk of developing endometrial cancer is 1.7%-2.6%. Endometrial cancer classically presents with postmenopausal bleeding (bleeding after the menopause), or intermenstrual bleeding (bleeding between periods).

It is well recognised, that cancer has a huge detrimental psychological effect. Few studies have investigated stress and anxiety levels in patients with suspected cancer, though it is assumed to be high.

1.2 RATIONALE FOR CURRENT STUDY

It is assumed that women attending rapid access clinics with suspected cancer are anxious and stressed but few studies have investigated this.

2. STUDY OBJECTIVES

Objectives:

- (1) Determine the anxiety levels of women with suspected endometrial cancer
- (2) Determine factors affecting anxiety levels

3. STUDY DESIGN

Paired observational study

Setting: Imperial College NHS Trust Hospitals, London

Participants: 250 women referred to rapid access clinic with postmenopausal bleeding or intermenstrual bleeding.

Duration: 1 year

3.1 MAIN STUDY

250 consecutive women presenting to the rapid access clinic with postmenopausal bleeding (PMB) and intermenstrual bleeding (IMB) will be approached for consent for inclusion into this study.

Women were given a short 5-minute questionnaire to fill during their first clinic attendance, before seeing any clinician or healthcare provider (see appendix for copy of questionnaire).

The questionnaire had 19 questions, split into 4 broad groups: questions quantifying anxiety/stress levels, factors that might affect anxiety levels, patient's perception of cancer diagnosis and the importance of a quick diagnosis. Patients were asked to score how they perceived their stress levels using a Likert scale. A score of 4 or above was defined as high stress in this study and 3 and below as low stress. Patients were also asked to fill a Generalised Anxiety Disorder 7 (GAD 7) form.

Women were excluded if, in the absence of a translator, they did not have sufficient comprehension of English to fill the questionnaire. Patients were also excluded from the analysis if they omitted 3 or more answers from the questionnaire.

For women needing a pipelle biopsy for clinical indications, the time taken to perform the biopsy, from insertion of the speculum to its removal was recorded in minutes, rounded to the nearest 30 seconds. Women were asked to rank their pain using a visual analogue score (0 to 10, where 0 is no pain and 10 is the worst pain in their life). Women were asked if they would have this procedure again, if they would recommend it to family or friends should they were need it. If women persisted with the procedure, they were asked their motivations for doing so, and what coping mechanisms they used. This paired data was matched to the patient's questionnaire responses.

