7. STATISTICS AND DATA ANALYSIS

Microsoft excel was used to provide the graphs and pie charts for demographics. SPSS version 25 was used to perform all the sub analyses. Median, quartile ranges, box and whiskers plots were created for each variable. A Mann-Whitney-Wilcoxon test was used to assess for association between each factor and anxiety as measured with GAD 7 score.

Data and all appropriate documentation will be stored for a minimum of 10 years after the completion of the study, including the follow-up period.

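### The high/low stress split at 4 has no stated reason, and the only association test named needs two groups, so relating stress to GAD-7 or biopsy pain with the stated tools would lose ordinal information

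*Combined protocol and SAP*

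**What the plan says.** Section 3.1 (Main study) collects a self-rated stress score: "Patients were asked to score how they perceived their stress levels using a Likert scale". It then fixes two categories: "A score of 4 or above was defined as high stress in this study and 3 and below as low stress". The number of scale points and their labels are not in the supplied text; the section refers to a questionnaire in an appendix that was not supplied. A second instrument is collected with no cut-point: "Patients were also asked to fill a Generalised Anxiety Disorder 7 (GAD 7) form".

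For women who have a biopsy, a 0–10 pain score, the duration and acceptability answers are recorded, and "This paired data was matched to the patient's questionnaire responses". No method is named for relating the two.

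Section 7 gives the analysis. Descriptively, "Median, quartile ranges, box and whiskers plots were created for each variable". For association, "A Mann-Whitney-Wilcoxon test was used to assess for association between each factor and anxiety as measured with GAD 7 score". No rank correlation, ordinal model or other method that uses all levels of a graded predictor is named. The synopsis gives the primary outcome as "Anxiety levels of women with suspected cancer", without naming an instrument.

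**The concern.** The split treats scores of 3 and 4 as opposites, and scores of 1 and 3 as the same. Mann-Whitney-Wilcoxon against GAD-7 compares GAD-7 between two groups. A graded stress score can enter as the predictor only once it has been grouped, and section 3.1 supplies the only grouping. The same holds for stress against the 0–10 pain score.

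If stress rises steadily with GAD-7 or with pain, the two-group comparison sees a weaker relation than the data contain and may miss it. The result also depends on a threshold for which the reader is given no reason. The graded score is already collected, so this loss can be avoided at almost no cost.

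**Working it through.** **Inputs from the documents.** Cut at 4 (section 3.1); Mann-Whitney-Wilcoxon against GAD-7 (section 7); 250 women to be approached (section 3.1). No significance level, power, effect size, score distribution or biopsy-subset size is given, so the plan has no figure to reproduce.

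**Assumed inputs.** 5-point scale; two-sided 5% test; 15%, 30% or 40% of women scoring 4 or above; latent correlation ρ of 0.20 or 0.40; biopsy subset of 100.

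**Step 1: normal-theory attenuation.** Splitting a normal score so that a proportion p is high multiplies its correlation by f = φ(z) / √(p(1−p)), where z is the upper-p normal quantile. Effective sample size is 250 × f².

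| p high | f | effective N out of 250 |
|---|---|---|
| 0.50 | 0.3989/0.5000 = 0.798 | 159 |
| 0.40 | 0.3863/0.4899 = 0.789 | 155 |
| 0.30 | 0.3477/0.4583 = 0.759 | 144 |
| 0.15 | 0.2332/0.3571 = 0.653 | 107 |

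The comparison here is with a continuous score. A 5-point score is already coarse, so this overstates the loss somewhat; step 3 corrects for that.

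**Step 2: approximate power of the split.** Power = Φ(atanh(ρf) × √(n−3) − 1.96), with √247 = 15.716 and √97 = 9.849.

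- n = 250, ρ = 0.20, p = 0.30: atanh(0.152) = 0.153; 0.153 × 15.716 − 1.96 = 0.44; power 0.67.
- n = 250, ρ = 0.20, p = 0.15: atanh(0.131) = 0.131; 0.131 × 15.716 − 1.96 = 0.10; power 0.54.
- n = 250, ρ = 0.40, p = 0.15: atanh(0.261) = 0.267; 0.267 × 15.716 − 1.96 = 2.24; power 0.99.
- n = 100, ρ = 0.40, p = 0.15: 0.267 × 9.849 − 1.96 = 0.67; power 0.75.
- n = 100, ρ = 0.40, p = 0.40: atanh(0.316) = 0.327; 0.327 × 9.849 − 1.96 = 1.26; power 0.90.

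**Step 3: simulation.** 2,000 data sets per setting; bivariate normal latent variables; stress cut to 5 levels; outcome a skewed 0–21 score. The same outcome shape stands in for pain in the n = 100 rows. Spearman on all levels is compared with Mann-Whitney on 4 or above.

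| n | ρ | p high | all levels | split |
|---|---|---|---|---|
| 250 | 0.20 | 0.15 | 0.81 | 0.53 |
| 250 | 0.20 | 0.30 | 0.83 | 0.65 |
| 250 | 0.20 | 0.40 | 0.83 | 0.68 |
| 100 | 0.20 | 0.15 | 0.43 | 0.25 |
| 100 | 0.20 | 0.30 | 0.47 | 0.31 |
| 100 | 0.20 | 0.40 | 0.46 | 0.34 |

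A second set of runs under the same scale, test level and range of p gave 0.81–0.83 against 0.53–0.66 (n = 250, ρ = 0.20) and 0.43–0.45 against 0.23–0.35 (n = 100, ρ = 0.20). The small differences are of the order of simulation error: √(0.66 × 0.34/2000) ≈ 0.01. The second set also covered ρ = 0.40: 1.00 against 0.99–1.00 at n = 250, and about 0.97 against 0.74–0.89 at n = 100. Those split figures agree with step 2.

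With ρ = 0, both methods rejected in about 5% of data sets (0.045–0.055).

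**The case against.** The strongest reply is that the plan never says it will test the high/low group. Section 7 tests factors against GAD-7, and section 3.1 lists the anxiety/stress questions separately from the factors that might affect anxiety, so stress may be a measure and not a factor. This stands in part: the loss is conditional on stress being related to GAD-7 or to the biopsy data. It does not remove the point, because the plan defines the split, matches the biopsy data to the questionnaire, and names no method that would relate the graded score to another graded measure. For a yes/no biopsy answer, a Mann-Whitney test could compare the graded stress score between answer groups without any cut, so the point concerns GAD-7 and pain.

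A reader might infer that the ordinal score is thrown away. It is not: it is collected, and section 7 summarises every variable by median and quartiles. A reader might also call the cut arbitrary. The questionnaire was not supplied and 4 may match a labelled category, so one can say only that no reason appears in the text.

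It is also fair that perceived stress and GAD-7 are both self-reports and may correlate well above 0.20. At 0.40 and n = 250 the loss is negligible. That reply is weaker for pain, which is recorded only in women who need a biopsy, so the n = 250 figures do not apply there. Finally, the proportion with high stress is a readable summary and worth reporting.

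**Conclusion.** The point holds in a limited form. The split has no stated reason, and the association test named in section 7 would force its use if stress were related to GAD-7 or to pain. The consequence is a weaker apparent relation and lower power, not false positives.

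For GAD-7 at n = 250, the loss is roughly 15 to 28 percentage points of power at latent correlation 0.20 (0.83 − 0.68 to 0.81 − 0.53) and close to none at 0.40. For pain in an assumed subset of 100, power drops from about 0.43–0.47 to 0.23–0.35 at 0.20, and from about 0.97 to 0.74–0.89 at 0.40. The direction is secure for a monotone relation. The size is illustrative, because scale length, score distribution, correlation and subset size are all assumed.

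The documents do not support reading this as damage to the GAD-7 analysis in general: GAD-7 is kept as a score, and its comparisons with other factors are untouched. This is a cheap improvement, not an error that invalidates the plan.

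**What to change.** In section 3.1, state the number of points and their labels, and give the reason for the cut if there is one. Make the full ordinal score the analysed stress variable, and keep the proportion scoring 4 or above as a descriptive summary only.

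In section 7, add the count at each stress level, and relate the score to GAD-7 and to the biopsy pain score by Spearman or Kendall rank correlation with a 95% confidence interval. Report the number of women with biopsy data beside the pain result.

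The cost is wording in two sections, with the same data and no new collection. The downside is that a correlation is slightly less simple to present than a high/low comparison; the retained proportion largely covers that.

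### Excluding women on a count of three or more omitted answers is not tied to whether their GAD-7 or stress score can be computed, so usable scores can be lost and selection bias is possible

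*Combined protocol and SAP*

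**What the plan says.** The primary outcome in the summary at the front of the document is "Anxiety levels of women with suspected cancer". Section 3.1 describes the instrument: "The questionnaire had 19 questions, split into 4 broad groups: questions quantifying anxiety/stress levels, factors that might affect anxiety levels", with the other two groups covering the woman's perception of a cancer diagnosis and the importance of a quick one. It then defines a Likert stress score ("A score of 4 or above was defined as high stress in this study and 3 and below as low stress") and adds: "Patients were also asked to fill a Generalised Anxiety Disorder 7 (GAD 7) form".

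The analysis set is defined by one sentence in section 3.1: "Patients were also excluded from the analysis if they omitted 3 or more answers from the questionnaire".

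Section 7 states: "Median, quartile ranges, box and whiskers plots were created for each variable" and "A Mann-Whitney-Wilcoxon test was used to assess for association between each factor and anxiety as measured with GAD 7 score".

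The text does not say which answers count towards the three, whether the GAD-7 items are among the 19 questions, or how a partly completed GAD-7 is scored. It gives no missing-data method and no comparison of excluded with retained women. Section 3.1 refers to an appendix copy of the questionnaire, which is not in the text available for this review.

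**The concern.** The exclusion is from the analysis as a whole and is triggered by a count of blanks, whichever questions they fall on. Three of the four question groups do not measure anxiety. A woman who skips three opinion or background questions is lost even if her GAD-7 is complete. A woman who leaves one or two GAD-7 items blank stays in, with no rule for her score. The Likert stress item has the same problem: a woman who answered it can be dropped for three other omissions, and one who skipped it can be kept.

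The anxiety summary and every factor comparison would therefore describe women with at most two omissions, not all women whose anxiety was measured. Women fill in the form before seeing any clinician at a suspected-cancer clinic, and anxiety is the outcome. The plan gives no reason to assume that skipping is unrelated to anxiety and has no step to check it. If the two are related, the estimates are biased by an unknown amount in an unknown direction.

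**Working it through.** The plan has no figure to reproduce: it states no omission rate, no sample-size derivation and no allowance for exclusions.

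**Inputs from the documents.** 19 questions, the threshold of 3 omissions, and 250 women approached (section 3.1). The GAD-7 has 7 items.

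**Assumptions, none from the documents.** Omission per item p = 2%, 5% or 10%. Omissions are either independent or correlated within a woman at 0.1 across all items. A GAD-7 with at least 6 of 7 items answered counts as scoreable. High anxiety differs by 20 percentage points, in either direction, between excluded and retained women with a scoreable GAD-7.

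**Step 1: can usable scores be lost on both readings?** There are C(19,3) = 969 ways to omit exactly three of 19 answers.
- GAD-7 separate from the 19: none of the 969 touches the GAD-7.
- GAD-7 items among the 19: C(12,3) = 220 of 969 (22.7%) leave all seven items answered.

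So the answer is yes on either reading.

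**Step 2: share excluded.** Let X be the number of omissions on the 19 items. Under independence, X is Binomial(19, p). At 5%, P(X ≥ 3) = 1 − (0.3774 + 0.3774 + 0.1787) = 0.0665. With correlation 0.1, X is beta-binomial with a = 9p and b = 9(1 − p).

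| p | Independent | Correlated |
|---|---|---|
| 2% | 0.6% | 4.6% |
| 5% | 6.7% | 13.1% |
| 10% | 29.5% | 29.4% |

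**Step 3: what is lost and what is kept at 5%.** Under independence with a separate form, P(complete GAD-7) = 0.95^7 = 0.698 and P(at least 6 of 7) = 0.698 + 7 × 0.05 × 0.95^6 = 0.956. The number recoverable is 250 × 0.0665 × 0.956 = 15.9. The other columns use the joint distribution in the same way.

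| At p = 5% | Indep., separate | Indep., among the 19 | Corr., separate | Corr., among the 19 |
|---|---|---|---|---|
| Excluded women with complete GAD-7 | 70% | 21% | 33% | 14% |
| Excluded women with at least 6 of 7 | 96% | 66% | 66% | 50% |
| Such women per 250 returned | 15.9 | 11.0 | 21.6 | 16.5 |
| Retained women with any GAD-7 item missing | 30% | 27% | 18% | 15% |
| Retained women with fewer than 6 of 7 | 4.4% | 2.4% | 3.7% | 1.4% |

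At 2% the recoverable numbers per 250 are 1.5 and 1.1 under independence, and 8.1 and 6.1 with correlation. Since 250 is the number approached, fewer questionnaires may be returned.

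**Step 4: shift that the fix would remove.** Let E be the share of all women who are excluded with at least 6 of 7 items answered, and R the share retained with at least 6 of 7. Then shift = 20 × E/(E + R) points. At 5%, independent, separate form: 20 × 0.0636/(0.0636 + 0.8920) = 1.33.

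| p | Indep., separate / among the 19 | Corr., separate / among the 19 |
|---|---|---|
| 2% | 0.12 / 0.08 | 0.66 / 0.50 |
| 5% | 1.33 / 0.92 | 1.88 / 1.43 |
| 10% | 5.89 / 4.23 | 4.25 / 3.31 |

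If the assumed 20-point difference is zero, every entry is zero.

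**The case against.** The strongest reply is that no consequence has been shown. The documents give no omission rate and nothing linking skipping to anxiety. The form is described as short, taking five minutes in clinic, so few omissions are plausible. At 2% with independence the rule removes about 1.5 women per 250 and the assumed shift is about 0.1 point. Even the largest shift above, 5.9 points, is just under the 95% half-width for a 40% proportion at n = 250: 1.96 × √(0.4 × 0.6/250) = 6.1 points. This stands as a limit on the size of the concern. It does not remove it, because bias adds to sampling error and the plan has no step that would reveal it.

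A second reply is that the reverse error looks large only when any missing item counts. Under a 6-of-7 rule, only 1.4% to 4.4% of retained women would be unscoreable at 5%. That is correct. But the plan states no such rule, so without one the analyst must improvise for the 15% to 30% with at least one item missing, or drop them.

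A third is that the appendix may show which items count or how the form is scored. It may, and the extent depends heavily on that. A list of items would still not tie a count of omissions to whether the score exists.

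Finally, a fixed completeness threshold is transparent and gives one common analysis set. That is a real advantage and is lost under the fix, but this common set does not guarantee a complete GAD-7.

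**Conclusion.** The concern holds. The text alone shows that the rule selects on the number of blanks and not on whether the outcome was measured, and nothing elsewhere in the document repairs this. Its size cannot be found from the documents. Over assumed omission rates of 2% to 5% per item, between about 1 and 22 women per 250 returned questionnaires would be dropped with at least 6 of 7 GAD-7 items answered. With an assumed 20-point difference, the removable shift in the share with high anxiety is about 0.1 to 1.9 points over that range, and 3.3 to 5.9 points at 10% omission. It is zero if skipping is unrelated to anxiety. Bias from women whose GAD-7 cannot be scored would remain under any rule of this kind. The change should be made because it is cheap and bears on the primary outcome, not because harm has been demonstrated.

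**What to change.** Amend sections 3.1 and 7 as follows.

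1. Estimate anxiety levels in every consenting woman with a scoreable GAD-7, and state the scoring rule for partly completed forms. One option is at least 6 of 7 items answered, with the missing item set to her mean of the other six. Summarise the Likert stress score in every woman who answered that item.
2. Run each Mann-Whitney-Wilcoxon comparison in every woman with a scoreable GAD-7 and an answer to the factor concerned.
3. Keep the three-omission rule only as a sensitivity analysis, and say which items it counts.
4. Report the numbers approached, consented, excluded and analysed. Compare GAD-7 scores between women whom the three-omission rule would exclude and the rest.

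The cost is a wording change, with no further patients or data collection. Sections 3.1 and 7 are partly in the past tense, so if the analysis has been done it must be re-run. That requires the excluded women's answers to have been kept, which the document does not state. The price is that the single common analysis set is lost and denominators differ between factors, so each comparison should report its own number of women.

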4. PARTICIPANT ENTRY

4.1 PRE-REGISTRATION EVALUATIONS

No need for any specific screening tests prior to participant entry into the study.

4.2 INCLUSION CRITERIA

All women presenting to rapid access gynaecology clinic with postmenopausal bleeding or intermenstrual bleeding

4.3 EXCLUSION CRITERIA

Anyone lacking capacity. <18years old. Pregnant. Any contra-indication carry out a biopsy

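### The biopsy contra-indication exclusion covers the whole study although the anxiety objectives need no biopsy; it should limit only the biopsy analyses

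*Combined protocol and SAP*

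**What the plan says.** The synopsis and section 4.3 list "Any contra-indication carry out a biopsy" alongside lack of capacity, age under 18 and pregnancy. Neither place limits it to part of the study, and no reason is given for it.

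The first objective in section 2 is "Determine the anxiety levels of women with suspected endometrial cancer"; the second concerns the factors that affect anxiety. The synopsis gives the primary outcome as "Anxiety levels of women with suspected cancer", and the secondary outcome is again about anxiety. The one test named in section 7 relates each factor to the GAD-7 score.

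Section 3 calls the design a "Paired observational study". Section 3.1 explains the pairing: biopsy time, pain and acceptability are recorded where a pipelle biopsy is clinically needed, and are matched to that woman's questionnaire. The questionnaire is filled in at the first attendance, before any clinician is seen. The GAD-7 form is described in the same paragraph, with no separate time given. Section 4.1 requires no specific screening tests before entry.

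On numbers, section 3 lists as participants "250 women referred to rapid access clinic with postmenopausal bleeding or intermenstrual bleeding", whereas section 3.1 says that "250 consecutive women presenting to the rapid access clinic" with these symptoms "will be approached for consent for inclusion into this study".

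**The concern.** An eligibility criterion should serve the question being asked. This one serves the biopsy component, which appears in neither the objectives nor the outcome measures, yet it decides who contributes to the primary outcome. The rationale in section 1.2 is the assumption that "women attending rapid access clinics with suspected cancer are anxious and stressed"; a woman who cannot have a biopsy belongs to that group as much as any other.

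Two things are at stake. The first is scope: the anxiety estimate describes a narrower group than the one named in section 2. The second is practical: if a contra-indication is recognised only in the consultation, the woman has already completed the questionnaire. She is then ineligible as the criterion is written, and usable anxiety data would be dropped for a reason unrelated to their validity.

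**Working it through.** **Is the exclusion needed for the stated aims?**

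1. Objectives, outcomes and named test (section 2, synopsis, section 7): all concern anxiety. None uses a biopsy result.
2. Measurement (section 3.1): self-completed questionnaire and GAD-7 form. No biopsy is required.
3. Pairing (sections 3 and 3.1): biopsy data come only from women biopsied on clinical indication. No section removes women who need no biopsy, so they stay in with questionnaire data only. A woman with a contra-indication could do the same, so the paired design does not require the exclusion.
4. Timing (sections 3.1 and 4.1): the questionnaire precedes clinician contact and no screening tests are required. No section says how or when a contra-indication is identified. Section 4.4 covers only withdrawal by choice or loss of capacity, and the analysis exclusion in section 3.1 covers only three or more omitted answers. The handling of data already collected from such a woman is not stated.

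**How much could it matter?**

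The plan gives no figure to reproduce here: 250 is stated without a derivation, and no frequency of contra-indications is given. Let s be the share of otherwise eligible attenders with a contra-indication. Assumption, not in the documents: s runs from near 0 to 10%, with 2% and 10% worked below.

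*Numbers affected.*
- Reading A, 250 counted before exclusions: excluded = 250 × s = 5 (2%) or 25 (10%); analysed n = 245 or 225.
- Reading B, 250 counted after exclusions: passed over = 250 × s/(1 − s) = 5.1 (2%) or 27.8 (10%); analysed n = 250.

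*Worst-case shift.* Suppose every excluded woman lies on the same side of the median. The median of the included women then sits at percentile 50 × (1 − s) or 50 × (1 + s) of all attenders: 49 or 51 at 2%, 45 or 55 at 10%. The shift is 50 × s, that is 1 to 5 points, under either reading.

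*Sampling error on the same scale.* The 95% half-width of a median is 100 × 1.96 × √(0.25/n) = 98/√n in percentiles of the included women. In this worst case, multiplying by (1 − s) converts it to percentiles of all attenders.

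| s | Shift | Half-width, A | Half-width, B |
|---|---|---|---|
| 2% | 1.0 | 0.98 × 98/√245 = 6.14 | 0.98 × 98/√250 = 6.07 |
| 10% | 5.0 | 0.90 × 98/√225 = 5.88 | 0.90 × 98/√250 = 5.58 |

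*Break-even.*
- A: 50s = (1 − s) × 98/√(250(1 − s)) = 6.198 × √(1 − s). Squaring, 2500s² + 38.42s − 38.42 = 0, so s ≈ 11.7%.
- B: 50s = 6.198 × (1 − s), so s = 6.198/56.198 ≈ 11.0%.

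*A proportion instead of a median.* Bias = s × (value in included − value in excluded women). With an assumed 20-point difference, s = 1%, 5% and 10% give 0.2, 1.0 and 2.0 points. The half-width for a proportion of 50% with n = 250 is 100 × 1.96 × √(0.25/250) = 6.2 points.

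These figures ignore non-consent and questionnaires dropped for omissions, both of which lower n and widen the half-width.

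**The case against.** Every exclusion narrows a target population, and section 4.3 gives no reason for any of its criteria, so singling out one may look like preference. Enrolling only women who could contribute to both parts of a paired study is also a coherent choice. That is fair as far as it goes: the choice is defensible in principle. But section 3.1 does not follow it through, since women who need no biopsy are kept without paired data. The criterion removes one group without biopsy data and leaves another in.

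A second objection is that the timing in sections 3.1 and 4.1 may mean that few women are kept out before giving anxiety data, so the restriction may be slight in practice. This stands as a limit on size. It also exposes the gap: the plan does not say what happens to a questionnaire already completed.

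Third, the share has no basis in the documents. Beyond the pregnancy, age and capacity exclusions, with which it may overlap, the criterion might exclude almost no one. This stands in full.

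A reader might infer that the documents contradict themselves, because section 4.2 admits all women with the presenting symptoms and section 4.3 then removes some. They do not: an exclusion may properly narrow an inclusion criterion. A reader might also infer that the anxiety estimate is biased. The documents give no evidence that anxiety differs in women with a contra-indication.

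**Conclusion.** The point holds as a question of scope and of avoidable data loss. The exclusion is study-wide, the anxiety aims do not need it, and the paired design does not require it. It is worth considering because the change is easy, not because a wrong result has been shown.

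The effect is probably small, its direction is unknown, and it may be close to nil. Under the assumed share of up to 10%, even the worst case moves the median by no more than 5 percentile points of all attenders. That is inside the sampling half-width of about 5.9 points (250 before exclusions) or 5.6 points (after). The worst case would exceed sampling error only above a share of about 11.7% or 11.0% respectively. The conclusion on scope rests on the text alone; the conclusion on size rests on the assumed share.

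**What to change.** **If recruitment is open:** amend the synopsis and section 4.3 so that the contra-indication criterion limits only the linked analyses of biopsy time, pain and acceptability. Analyse GAD-7 in all consenting, otherwise eligible women. Who receives a biopsy does not change. The cost is one wording amendment to a protocol that already has ethics approval (section 8.1), with no added procedure.

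**If recruitment is complete**, as the past tense in much of sections 3.1 and 7 suggests it may be: state in the report that the anxiety estimate applies to women without a biopsy contra-indication, and give the number excluded on this criterion if it was recorded (no screening log is described). Use questionnaires already collected from excluded women only if the ethics approval and their consent (sections 8.1 and 8.2) cover it, and then only as a labelled sensitivity analysis beside the main analysis as specified. The cost is a sentence and, where available, a count. Women never enrolled cannot be recovered.
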